## 11.5 Planned Interim Analyses

Interim analyses will only be used to terminate this trial in the event that unanticipated safety events deemed to be of sufficient concern require such action by the sponsor. These assessments will not be made on the basis of testing a formal statistical hypothesis; therefore, p-value adjustment will not be made to any analyses. A DSMB will be convened by DMID to review study progress and participant, clinical, safety, reactogenicity and immunogenicity data as described in [Section 9.6.2](#).

Clinical, safety, and reactogenicity data through approximately 56 days after study vaccination will represent the interim clinical database for this trial. Once the last subject completes the visit that occurs approximately 56 days after first study vaccination, the interim clinical database will be cleaned, monitored and locked. Upon receipt of immunogenicity data for Day 1 and Day 29 (HAI, NAI, and Neut data) and safety data through Day 57, the sponsor will authorize the DCC to transfer to Sanofi Pasteur a copy of this unblinded data set. An expedited report containing analyses of safety data through Day 57 and HAI, NAI, and Neut data from baseline (Day 1) and Day 29 unblinded by treatment group only will be prepared by the SDCC. These analyses may be made available to the sponsor and pharmaceutical partners for planning subsequent trials as

well as the DSMB for review. Other immunological analyses that are available may also be included in the expedited report and may also be reviewed by the DSMB.

The analyses performed for the expedited report or using the data set provided to Sanofi Pasteur will not be used to make any decisions concerning the conduct of this trial. As it is anticipated that subjects will remain in long term safety follow-up at the time of these analyses, blinded investigators and DMID medical monitors not involved in the analysis, publication, or clinical study report preparation will be responsible for assessing SAEs and AESIs (including Protocol Specified AESIs, MAAEs, NOCMCs and PIMMCs) until all subjects have completed the final follow-up visit.

### **11.5.1 Interim Safety Review**

An interim safety review may include enrollment and demographic information, medical history, concomitant medications, physical assessments, clinical laboratory values, dosing compliance, and solicited and unsolicited AE/SAEs. Additional data may be requested by the DSMB, and interim statistical reports may be generated as deemed necessary and appropriate by DMID. The DSMB may receive data in aggregate and presented by treatment arm, including expected and observed rates of the expected AEs. The DSMB will review grouped data in the closed session only. The DSMB will meet and review these data at scheduled time points or ad hoc as needed during this trial as defined in the DSMB charter. As an outcome of each review/meeting, the DSMB will make a recommendation as to the advisability of proceeding with study vaccinations (as applicable), and to continue, modify, or terminate this trial.

Additionally, this trial will be monitored to determine if any of the halting rules described in [Section 9.5](#) are met.

### **11.6 Final Analysis Plan**

Subject unblinding will occur and the final CSR will be completed after the last subject's last visit is completed, the final clinical database including all long-term safety follow-up data is cleaned, monitored and locked, and all primary and secondary immunogenicity data are available. After such data are reported in the database and the data are considered clean and complete, a "topline" subset of the immunogenicity tables planned for the CSR will be provided to DMID and Sanofi Pasteur. Additional exploratory immunogenicity endpoint data not available at the time of CSR preparation may be included in an addendum to the CSR, manuscript(s), or other report.

A formal statistical analysis plan which defines the analyses to be included in the expedited report and the final CSR will be developed, finalized, and submitted to the FDA, prior to unblinding for any analysis.

### **11.6.1 Analysis Populations**

The Safety Analysis population includes all subjects who received the first dose of study vaccine.

The modified intent-to-treat (mITT) population includes all randomized subjects who received the first dose of study vaccine and contributed at least one post-first study vaccination venous blood samples for immunogenicity testing (HAI, NAI or Neut antibody assays) for which valid results were reported. For analyses using the mITT population, subjects will be grouped based on randomized treatment arm.

The per protocol (PP) population includes all subjects in the mITT with the following exclusions:

- Data from all available visits for subjects found to be ineligible at baseline.
- Data from all visits for subjects that did not contribute venous blood samples for immunogenicity testing (HAI, NAI or Neut antibody assays) at baseline (Day 1).
- Data from all visits subsequent to major protocol deviations, such as:
  - Receipt of non-study licensed live vaccine within 30 days before or after the first study vaccination,
  - Receipt of non-study licensed inactivated vaccine within 14 days before or after the first study vaccination,
  - Receipt of immunosuppressive therapy (e.g., corticosteroids) within 30 days before or after the first study vaccination.
- Data from any visit that occurs substantially out of window.

For analyses using the PP population, subjects will be grouped based on study vaccinations received.

### **11.6.2 Safety Data**

Summaries and analysis of safety data will be presented for the Safety Analysis Population. All summaries and analyses will be presented for all subjects.

Solicited AEs will be summarized by severity after the first study vaccination (1-7 days post study vaccination) and as the maximum severity over all 8 days. Additionally, solicited AEs will be analyzed by taking the most severe response over the follow-up period, dichotomizing into a binary variable (none versus mild, moderate, or severe) and using standard techniques, such as exact confidence intervals, to summarize the proportion of subjects reporting each symptom, any injection site symptom, and any systemic symptom. Summaries of solicited AEs will be presented for the first study vaccination by treatment arm. The proportion of subjects reporting symptoms may be compared between treatment arms using Chi-square or Fisher's exact test. Unsolicited AEs will be coded by Medical Dictionary for Regulatory Activities (MedDRA®) for preferred term and system organ class (SOC). The numbers of SAEs and AESIs (including Protocol Specified AESIs, MAAEs, NOCMCs and PIMMCs) are likely to be small in this trial and will be reported by detailed listings showing the event description, MedDRA® preferred term and SOC, relevant dates (study vaccinations and AEs), severity, relatedness, and outcome for each event. Non-serious unsolicited AEs will be summarized as number and percentage of subjects reporting at least one event in each MedDRA® preferred term and SOC, cross tabulated by severity and relationship to study product. Additionally, the proportion of subjects and exact 95% confidence intervals of AEs in aggregate and by MedDRA® categories will be computed. Clinical laboratory data will be summarized by severity for each visit and as the maximum over all post-study vaccination visits. Graphical presentations may include box plots.

### **11.6.3 Humoral Immunogenicity Data**

Summaries and analysis of immunogenicity data will be presented for the mITT and PP populations.

Immune responses in terms of strain-specific HAI, NAI, and Neut antibody titers will be summarized by treatment arm at each time point. Analyses will include GMTs, ratio of GMTs between adjuvanted and unadjuvanted study arms, percentage of subjects achieving seroconversion (as defined in Table 1) and percentage of subjects with a titer  $\geq 1:40$  (HAI and Neut only) along with corresponding 95% confidence intervals. Descriptive summary statistics will be provided for all assays and time points. These immune responses against vaccine strains will also be presented by serostatus and previous influenza vaccination. The correlation between

HAI, NAI and Neut antibody titers will be evaluated. Plots such as reverse cumulative distributions or longitudinal presentations of GMTs will be presented.

Further immunogenicity testing and/or analyses may be carried out in the future based upon subjects' prior receipt of non-seasonal influenza vaccines, including type (inactivated or live attenuated), what subtype (e.g. A/H3, A/H5, A/H9) and approximate date of vaccination.

#### **11.6.4 Exploratory Cellular Immunogenicity Data**

Summaries of exploratory cellular immunology assays will be presented for the Per Protocol Population and will be presented overall as well as by treatment arm.

Analysis of the exploratory cellular immunogenicity data will be primarily descriptive. Association of exploratory endpoints with HAI, NAI, and Neut antibody titers will be assessed.

#### **11.6.5 Exploratory Transcriptomics Data**

For the transcriptomics exploratory analysis, RNA-Seq data will be pre-processed by removing adapters and low-quality reads and mapping sequences to the latest human reference genome using splice-aware alignment software such as *HISAT2* [52]. Gene expression quantification will be carried out by using the *Subread* software [53] using the latest Ensembl [54] gene model annotations as a reference. Systematic differences in sequence coverage between samples will be accounted for using the TMM normalization method [55] as implemented in the *edgeR* R package [56]. Principal component analysis, non-metric multidimensional scaling, and hierarchical clustering analysis will be used to identify potential outliers and systematic batch effects. Negative binomial models as implemented in *edgeR* [56] will be used to identify genes for each study group and post-vaccination day (Day 2 and 8) that were differentially expressed (DE) compared to pre-vaccination. If the analysis reveals a systematic batch effect that is not associated with study group or study visit, it will be accounted for by adding a batch blocking factor as part of the negative binomial models. To control for testing multiple genes, the false-discovery rate (FDR) based on the Benjamini-Hochberg procedure [57] as implemented in the *p.adjust* R function will be applied. The *pvclust* R package [58] will be used to identify co-expressed DE gene clusters. Mean cluster log2 fold change time trends and associated 95% bootstrap CIs will be presented by group across post-vaccination days. To functionally characterize DE genes, pathway enrichment analysis based on the latest MSigDB [59] and KEGG [60] databases as well as Blood Transcription Modules [61] will be carried out using the implementation provided by the *goseq* R package [62] which accounts for gene length bias. Pathway maps color-coded by treatment effect (log2 fold change compared to pre-vaccination)

will be visualized for significantly enriched KEGG pathways. Pathway enrichment trends by group across post-vaccination days will be visualized using heatmaps and time trend plots of median pathway responses (based on median average  $\log_2$  fold changes of all pathway members) and associated 95% bootstrap CIs. Regularized linear regression analysis as implemented in the glmnet R package [63] will be utilized to identify gene expression changes that are predictive of later adaptive humoral immune response. Cross-validation will be used to select optimal models.

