## **11 STATISTICAL CONSIDERATIONS**

### **11.1 Introduction**

The goal of this clinical study is to assess, in healthy adults ages 18-45, the safety, reactogenicity and immunogenicity of either the 2018/2019 seasonal Fluzone or Flublok QIV manufactured by Sanofi Pasteur administered intramuscularly given without adjuvant or with one of two adjuvants, AF03 or Advax-CpG55.2. These study arms are included to allow evaluation of the potential of each of the two adjuvants to enhance the immune response to either the 2018/2019 seasonal Fluzone QIV or the 2018/2019 seasonal Flublok QIV.

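### Protocol 11.6.5 tests gene expression only as change from baseline within each arm; no between-arm contrast of that change is specified, so the transcriptomics plan neither estimates nor tests an adjuvant effect

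*Protocol*

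**What the plan says.** The only gene-level test in Protocol 11.6.5 is the one that will "identify genes for each study group and post-vaccination day (Day 2 and 8) that were differentially expressed (DE) compared to pre-vaccination". With six groups and two days, that gives 6 x 2 = 12 within-group comparisons. Multiplicity is handled as follows: "To control for testing multiple genes, the false-discovery rate (FDR) based on the Benjamini-Hochberg procedure" will be applied. No FDR level is given, and the section does not say whether the procedure runs within each comparison or across all 12.

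The later steps also work on within-group change:

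- Clusters: "fold change time trends and associated 95% bootstrap CIs will be presented by group across post-vaccination days".
- Pathways: "Pathway enrichment trends by group across post-vaccination days will be visualized using heatmaps and time trend plots of median pathway responses", also with bootstrap intervals.
- Maps: "Pathway maps color-coded by treatment effect", where the parenthesis that follows defines that effect as the log2 fold change against pre-vaccination.
- Regularised regression: used to "identify gene expression changes that are predictive of later adaptive humoral immune response", with no arm contrast stated.

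Protocol Table 1 frames the transcriptomic objective as response from Day 1 to Days 2 and 8, in an unspecified subset of each group at minimum. The SAP Preface says that the SAP covers every planned analysis apart from transcriptomics, so 11.6.5 is the only specification of methods. Protocol 11.1 states that the arms allow "evaluation of the potential of each of the two adjuvants to enhance the immune response" to each vaccine. For antibody titers, Protocol 11.6.3 plans the matching between-arm quantity, a ratio of GMTs of adjuvanted to unadjuvanted arms.

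**The concern.** Whether AF03 or Advax-CpG55.2 changes the transcriptional response to a given vaccine is a question about the difference between two arms. All six arms receive a vaccine on Day 1 and there is no placebo arm. The pre-to-post change in an adjuvanted arm therefore combines the response to the vaccine, whatever the adjuvant adds, and anything else that differs between visits. The adjuvant's part is isolated only by the randomised comparison with the unadjuvanted arm that received the same vaccine.

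Without that contrast, a reader who wants an adjuvant signature has to set within-arm results side by side. Where this is done with gene lists, a gene that passes the FDR cut in one arm and misses it in the other may be taken as adjuvant-specific, although that pattern is not evidence of a difference. Calling the within-arm change a treatment effect invites this reading.

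**Working it through.** The plan states no sample size, power or FDR level for transcriptomics, so it has no figure to reproduce. What can be checked is how often equal responses would look arm-specific if lists were compared.

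**1. Analytic check.** Take one gene with the same true change in two independent arms, and let w be the probability that it passes the cut in either arm.

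- Significant in exactly one arm: w(1-w) + (1-w)w = 2w(1-w).
- Significant in at least one arm: 1-(1-w)^2.
- Spuriously arm-specific share of the genes that appear on either list: 2w(1-w) / [1-(1-w)^2].

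| w (assumed) | exactly one arm | at least one arm | share |
|---|---|---|---|
| 0.2 | 2 x 0.2 x 0.8 = 0.32 | 0.36 | 89% |
| 0.5 | 2 x 0.5 x 0.5 = 0.50 | 0.75 | 67% |
| 0.8 | 2 x 0.8 x 0.2 = 0.32 | 0.96 | 33% |
| 0.9 | 2 x 0.9 x 0.1 = 0.18 | 0.99 | 18% |
| 0.95 | 2 x 0.95 x 0.05 = 0.095 | 0.9975 | 9.5% |

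**2. Simulation with whole gene lists.** The inputs are assumptions, apart from the upper sample size of 40 per group (Protocol 11.4.2):

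- 12,000 independent genes, of which 10% or 30% respond;
- standardised changes drawn from a normal distribution with SD 0.3, 0.5 or 0.8, identical in both arms;
- 10, 20 or 40 subjects per arm;
- paired t-tests with Benjamini-Hochberg at 5% in each arm, a normal model in place of the negative binomial, and 20 replicates.

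There was no true arm difference in any scenario.

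| n per arm | genes on the second arm's list only | as share of that list | genes called by the direct contrast |
|---|---|---|---|
| 40 | 57 to 398 | 16% to 60% | 0 to 0.15 |
| 20 | 5 to 395 | 25% to 94% | 0 to 0.20 |

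At n = 10 the lists ranged from empty to about 600 genes, so shares there are unstable. The direct contrast averaged 0 to 0.10 genes.

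The direct contrast is the difference between the two arms' changes, with Benjamini-Hochberg at 5%. Its near-zero count shows that it does not produce false differences. It says nothing about power. With equal numbers and variances, the standard error of the difference is sqrt(2), about 1.41, times that of one arm's change, so only larger adjuvant effects will be found.

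**3. Count of missing contrasts.** Four adjuvanted arms (Groups 2 and 3 against Group 1; Groups 5 and 6 against Group 4) at two days give 4 x 2 = 8.

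**The case against.** The best defence is that 11.6.5 does what its objective asks. Table 1 asks for response from baseline, the design description links expression to antibody response within the arms, and Protocol 11.2 and SAP 6.8 say that the study is not built around formal hypothesis tests. The sentence in 11.1 concerns the immune response in general, and the GMT ratios already serve it. No passage plans overlap counts or a claim that a gene belongs to one arm. All of this stands, and it is why the point concerns an omission in an exploratory analysis and not an invalid planned inference.

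A reader might also infer more than the documents support:

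- That an adjuvant signature could be read only from gene lists. By-group fold changes with intervals are planned for clusters and pathways. The pathway medians use all members of a pathway, so they do not depend on which genes passed the cut, and the 2w(1-w) argument does not apply to them.
- That clustering is done separately in each arm. The text says that cluster trends are displayed by group; one common set of clusters fits the wording equally well.
- That a third to a half of responding genes will look arm-specific. That range belongs to per-arm power of about 0.2 to 0.8 and falls to 9.5% at 0.95.

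The planned intervals still leave the gap open. Each describes one arm's change. Judging two separate intervals by eye neither estimates nor tests the difference, and the clusters are formed from genes already selected as differentially expressed.

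**Conclusion.** The point holds in a limited form. No between-arm contrast of change from baseline is specified in Protocol 11.6.5, in Table 1 or in the SAP. The by-group lists and side-by-side fold changes permit an informal comparison of size but no estimate or test of what an adjuvant adds. The section is consistent with its own from-baseline objective; the shortfall is against the purpose of the arms in 11.1.

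If lists are compared, the chance that an equally responding gene appears in exactly one of two arms runs from 9.5% to 50% over per-arm power of 0.2 to 0.95. This rests on independent arms, equal true effects and an assumed power. The simulated shares rest further on assumed effect sizes, numbers and a 5% FDR. The documents do not settle which values apply, nor do they show that such a comparison will be reported. The point is worth acting on because the remedy is cheap, and it does not affect the primary or secondary analyses.

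**What to change.** In Protocol 11.6.5, fit all arms in one edgeR model that accounts for the repeated samples per subject (for example, subject as a blocking factor with arm-by-day terms). Add the contrast

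(post - pre, adjuvanted arm) - (post - pre, unadjuvanted arm with the same vaccine)

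for each of the four adjuvanted arms at Days 2 and 8, eight contrasts in all. Apply Benjamini-Hochberg at a stated FDR level, and say whether the family is one contrast or all eight. Run the pathway enrichment on these contrasts as well. Keep the within-arm results as description, and call the fold change against pre-vaccination a change from baseline, not a treatment effect. State that the analysis remains exploratory.

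The cost is a few sentences in 11.6.5 and some added programming within the planned edgeR framework. No new samples, visits or assays are needed.

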#### **7.2.3.2 Specimen Shipment**

Specimen shipment will occur at intervals during the course of this trial following all applicable International Air Transport Association (IATA) requirements and according to the specifics for storage temperature and documentation as detailed in the central (clinical) laboratory manual and protocol-specific MOP as appropriate.

Specimens for clinical safety laboratory evaluations will be shipped from the participating VTEU sites to the central (clinical) laboratory except those done locally.

Specimens for antibody, cellular and transcriptomic assays will be shipped from the participating VTEU as outlined in the MOP.

Further instructions for specimen shipment are included in the central (clinical) laboratory manual and protocol-specific MOP, as appropriate.

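### The transcriptomics plan adjusts for batch when batch is unrelated to group or visit, but gives no rule for a batch partly associated with visit, where leaving it out biases the fold changes

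*Protocol*

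**What the plan says.** Protocol 11.6.5 (Exploratory Transcriptomics Data) fits negative binomial models for each study group and for Days 2 and 8, to find genes "that were differentially expressed (DE) compared to pre-vaccination". The contrast is therefore between visits, within a group.

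Batch appears twice in that section. First, principal components, non-metric multidimensional scaling and hierarchical clustering "will be used to identify potential outliers and systematic batch effects". Second comes the adjustment rule: "systematic batch effect that is not associated with study group or study visit, it will be accounted for by adding a batch blocking factor". Nothing is said about a batch effect that is associated with group or visit: no adjustment, no sensitivity analysis and no reporting caveat.

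The SAP's Preface states that it covers the planned analyses other than transcriptomics, so it adds no rule. Protocol 7.2.2 says that the whole-blood samples go to the sponsor partner's research laboratories and leaves preparation and shipping to the manual of procedures. Protocol 7.2.3.2 adds, for specimens generally, "Specimen shipment will occur at intervals during the course of this trial". Neither section describes how RNA samples are allocated to library or sequencing batches.

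**The concern.** A blocking factor does different work in three situations.

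- **Batch unrelated to visit.** Leaving it out adds noise but does not bias the visit contrast. Adjusting gains precision. This is the situation for which 11.6.5 provides.
- **Batch partly associated with visit.** Suppose more Day 1 tubes are in one run and more Day 8 tubes in another. Without the factor, the post-versus-pre fold change absorbs part of the difference between runs. With it, the visit effect is still estimable. 11.6.5 does not provide for this situation.
- **Batch fully confounded with visit.** The two cannot be separated, and no model term helps.

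The condition in 11.6.5 thus supplies the adjustment where it is least needed and withholds a rule where it matters most. Genes that differ only by run could be reported as responding to vaccine or adjuvant. They would then pass into the co-expression clusters and pathway enrichment, and the shifted expression changes would enter the regularized models that predict the antibody response. The planned error control ("To control for testing multiple genes, the false-discovery rate (FDR) based on the Benjamini-Hochberg procedure") does not help, because it assumes valid p-values and these would be biased.

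**Working it through.** The plan gives no sample size, power or batch size for transcriptomics, so there is no figure to reproduce. The check is of the logic, with illustrative sizes.

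**1. Bias for one gene with no true change.** Let b be the batch effect in log2 units, and let q_pre and q_post be the shares of pre- and post-vaccination samples in the affected batch. If batch is omitted, the expected log2 fold change is

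log2[(q_post·2^b + 1 − q_post) / (q_pre·2^b + 1 − q_pre)].

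Example with b = 1, q_pre = 0.7 and q_post = 0.3: log2(1.3/1.7) = −0.39, where the truth is 0.

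**2. Negative binomial simulation of the same gene.** There were 1,500 replicates and 38 samples per visit. The 38 is borrowed from the number expected per group for the primary immunogenicity analysis (Protocol 11.4.2). Assumed because the documents give no values: mean count 200, dispersion 0.2, b from 0.5 to 1.0. Rejection is at nominal 0.05.

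| Batch share, pre/post | Bias if omitted (formula) | Rejection, batch omitted | Rejection, batch included |
|---|---|---|---|
| 50/50 | 0 | 0.050 to 0.021 | 0.060 to 0.062 |
| 60/40 | −0.10 to −0.19 | 0.085 to 0.155 | 0.055 to 0.060 |
| 70/30 | −0.20 to −0.39 | 0.25 to 0.60 | 0.049 |
| 80/20 | −0.30 to −0.59 | 0.43 to 0.91 | 0.055 to 0.058 |
| 100/0 | −0.5 to −1.0 | 0.91 to 1.00 | not estimable |

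With batch included, the mean estimate at 60/40 to 80/20 lies between −0.005 and +0.009. At 100/0 the design matrix has rank 2 of 3. The price of adjusting is visible at 80/20, where the SD of the estimate rises from about 0.15 to 0.185.

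**3. Association with group only.** With the batch share at 80% at both visits, or 20% at both visits, the simulated bias with batch omitted is within 0.01 of zero and rejection is 0.020 to 0.054. The within-group contrasts are not harmed.

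**4. Share of genes falsely called after false-discovery control.** This used 5,000 genes with no true change, 40 subjects per arm, paired log2 differences, per-sample SD 0.4 log2, a gene-specific batch shift with SD s, and Benjamini-Hochberg at 5%. All values except the 40 per arm are assumptions.

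| Batch share, Day 1/Day 8 | s = 0.2 | s = 0.3 | s = 0.5 |
|---|---|---|---|
| 70/30, batch omitted | 0.04% | 1.2% | 15.3% |
| 80/20, batch omitted | 4.9% | 20.7% | 47.9% |

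A repeat of this illustration with 40 per arm gave 0.1% to 17% at 70/30 and 8% to 47% at 80/20. At 60/40 the repeats gave about 0.2% or less. With batch in the model the figure was 0.01% or less throughout. These shares are lower than the rejection rates in step 2 because the false-discovery threshold is stricter than 0.05 and most genes have a smaller shift than b = 0.5 to 1.0.

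**5. Smaller samples.** Protocol Table 1 allows the profiling to cover only a subset of each group. With 20 per arm the falsely called share is 0.07% or less at 70/30 and 0.07% to 21% at 80/20.

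**The case against.** Several points on the other side stand.

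- **The text does not say *only*.** A reader might infer that the protocol instructs the analyst to drop batch when it is associated with visit. It does not: it states one case and is silent on the other. What can be said is that an analyst following the text has a rule for the harmless case and none for the harmful one, so that choice would be made after seeing the data.
- **The condition has a sensible purpose.** The protocol looks for batch effects in ordination and clustering plots ("Principal component analysis, non-metric multidimensional scaling, and hierarchical clustering analysis will be used to identify potential outliers and systematic batch effects"). A cluster that tracks visit in such a plot may be the vaccine response itself, and blocking on it would remove the signal. This is a good reason not to block on inferred clusters. It is not a reason to leave out a batch recorded by the laboratory. The condition also fits complete confounding, where adjustment is impossible.
- **Nothing shows that RNA tubes are batched by visit.** A reader might infer it from Protocol 7.2.2, where serum from Days 1 and 29 is shipped before Day 8 serum, but that schedule concerns serology. RNA is drawn on Days 1, 2 and 8 (Protocol Table 3), while enrollment takes about 9 weeks. If tubes were split into two batches by collection date, the batch share would shift between Day 1 and Day 8 by about 7/63 = 11 percentage points, against 40 points at 70/30. At that shift the falsely called share is 0.003% or less. The manual of procedures, which is not among these documents, may also specify a balanced layout.
- **The harm needs strong imbalance.** At 60/40 it is near zero after false-discovery control.
- **The illustration in step 4 uses paired log2 differences**, not the planned negative binomial model. Step 2 uses a negative binomial model and agrees on direction.

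**Conclusion.** The concern holds in a limited form. 11.6.5 makes batch adjustment conditional on no association with group or visit and states nothing for an associated batch. For the Day 2 and Day 8 contrasts, partial association with visit is the case where omission biases the result and where a blocking factor is both estimable and effective. That direction does not depend on the assumed values.

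The size does. It rests on an undocumented batch layout and on assumed batch shift, noise and sample size. It ranges from negligible at 60/40, through about 0.04% to 17% of genes at 70/30, to 5% to 48% at 80/20.

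Two stronger readings are not supported. The documents do not show that false calls will occur in this trial, because no visit-related batching is described. Nor does batch associated with group alone bias the planned contrasts, provided it is balanced over visits.

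The analysis is exploratory, and no primary or secondary endpoint is affected. The point is still worth settling before sequencing, because complete confounding cannot be repaired afterwards.

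**What to change.** Reword the batch rule in Protocol 11.6.5, or place it in a separate transcriptomics plan, as follows.

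- Include the recorded library or sequencing batch as a blocking factor in the negative binomial models whenever it is estimable, including when it is partly associated with visit.
- Do not treat a cluster seen only in principal components, scaling or clustering plots as a batch, since it may be vaccine response.
- If a visit is fully confounded with batch, report that contrast as not separable from batch. If batch is confounded with group only, keep the within-group contrasts, which remain valid.
- Where feasible, process each subject's Day 1, 2 and 8 tubes in the same batch, with arms balanced across batches, and say so in the laboratory instructions.

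The cost is a few sentences and a plate-layout instruction. Fold-change intervals become slightly wider where batch and visit overlap, and a subject's Day 1 tube waits a short time for the later ones.
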